5.3 LIFESTYLE CONSIDERATIONS

Subjects will be provided with Cetaphil Skin Cleanser, which is the only cleanser permitted during the conduct of the study and should be used as described in [Section 6.5.1](#).

Topical bland emollients (without pharmacological active ingredients) are allowed during the study, except within 3 hr prior to the study visit. Make-up, facial moisturizers, creams, lotions, and/or sunscreens are also allowed during the study, except within 3 hr prior to the study visit. Use of sunscreen products and protective apparel are recommended when sun exposure cannot be avoided.

For subjects who use emollients, make-up, facial moisturizers, creams, lotions, and/or sunscreens, the same product brands/types should be used at the same frequency throughout the study. Every effort should be made to keep the same products throughout the study. In case a subject applied these products on the face on a visit day, they will be instructed to wash their face with Cetaphil Skin Cleanser at least 3 hr before the visit and not reapply these products on the face before the visit.

Subjects should continue with their regular shaving habits (if applicable) during the study, but must not shave their face within 3 hr prior to study the visit.

Efficacy and Safety of Imsidolimab in Subjects with Acne Vulgaris
Protocol ANB019-209

Version 1.0
11 February 2021

5.4 SCREEN FAILURES

Screen failures are defined as subjects who consent/assent to participate in the clinical study but are not subsequently randomized in the study. A minimal set of screen failure information is required to ensure transparent reporting of screen failure subjects to meet the Consolidated Standards of Reporting Trials (CONSORT) publishing requirements and to respond to queries from regulatory authorities. Minimal information includes demography, screen failure reasons, eligibility criteria not met, and any SAE that occurred.

Individuals who do not meet the criteria for participation in this study (screen failure) may be rescreened once after discussion with the Medical Monitor. Rescreened subjects should not be assigned the same subject number as for the initial screening. All procedures planned at the screening visit, including signature of a new consent/assent form, will be performed.

5.5 STRATEGIES FOR RECRUITMENT AND RETENTION

The recruitment and retention strategies for the study will be covered in other study plans.

6 STUDY TREATMENT

Study treatment is defined as any investigational treatment or placebo intended to be administered to a clinical study subject according to the study protocol.

6.1 STUDY TREATMENT ADMINISTRATION

6.1.1 STUDY TREATMENT DESCRIPTION

Imsidolimab is a humanized IgG4 (S228P)/kappa mAb that belongs in the class of anti-IL-36R mAb. Details regarding imsidolimab and placebo study treatment are described in [Table 2](#) and further information will be provided in the Pharmacy Manual.

6.1.2 DOSING AND ADMINISTRATION

Study treatment dosing and administration details are provided in [Table 2](#). Further information will be provided in the Pharmacy Manual.

Table 2: Study Treatment Details

Study Treatment Name:	Imsidolimab (ANB019) Anti-interleukin 36 receptor monoclonal antibody	Placebo
Dosage Form:	Solution for injection	
Source of procurement:	AnaptysBio, Inc.	
Study Treatment Description	Imsidolimab will be provided as a sterile, colorless to yellow, and clear to slightly opalescent solution supplied in a single use, 2R, Type I glass vial with a fill volume of 1.2 mL. Each vial contains 120 mg of imsidolimab at a concentration of 100 mg/mL.	The placebo contains no active ingredient and will be provided as a sterile, colorless to slightly yellowish, and clear to very slightly opalescent solution supplied in a single use, 2R, Type I glass vial with a fill volume of 1.2 mL.
Dosage Formulation:	100 mg/mL imsidolimab in 25 mM-histidine, 60 mM-NaCl, 145 mM sorbitol, and 0.02% v/v polysorbate-20 at pH 6.0.	Placebo (25 mM-histidine, 60 mM-NaCl, 145 mM sorbitol, and 0.02% v/v polysorbate-20, at pH 6.0).
Unit Dose Strength(s)/ Dosage Level(s):	Study treatment will be administered as 400/200/100 mg of imsidolimab or placebo. 1 mL vials of active and placebo doses will be provided to sites and prepared by an unblinded pharmacist according to Table 3 .	
Route of Administration:	SC injection (3 doses during the treatment period)	
Dosing Instructions:	Imsidolimab and placebo should be administered by clinic staff trained in best practices for SC administration of study treatments.	

Efficacy and Safety of Imsidolimab in Subjects with Acne Vulgaris
Protocol ANB019-209

Version 1.0
11 February 2021

Study Treatment Name:	Imsidolimab (ANB019) Anti-interleukin 36 receptor monoclonal antibody	Placebo
	
For SC injections, imsidolimab and placebo should be prepared by drawing up the required dosing volume into suitable sized syringe and attaching a dosing needle. No further dilution is required. Syringes should be covered in tape by an unblinded pharmacist to obscure color and volume.
 
The preferred anatomical site of SC administration is the abdomen; however, the injection may be made in the upper arm, if needed.
 
A 30-minute observation period should be included after the first dose administered.
 
The same anatomical site should be used throughout the entire study for a given subject (ie, do not administer one dose into the upper arm and at a subsequent visit or dose, administer the next dose into the abdomen).
 
Subsequent doses should be rotated within an anatomical site (ie, if the upper left abdominal quadrant is used as the initial site of administration, then the next administration at a subsequent visit should be rotated to the upper right quadrant).
 
Subcutaneous injections should not be given into moles, scars, tattoos, or areas where the skin is tender, bruised, red, hard, or not intact.
 
Prior to SC needle insertion, the skin will be pinched between the thumb and index finger to separate the subcutaneous layer from the muscle.
 
The needle is to be injected at a 90-degree angle to the fat pad.
 
The plunger will be pressed gently until the entire dose is delivered to the SC space and the needle will be held in place (fully depressed) for 10 seconds after the injection is administered.
 
The needle will be removed and then the skin pinch released; any leakage or backflow of fluid from the administration site onto the surface of the skin will be noted and documented in the eCRF.
 
The site of administration is NOT to be massaged by either the clinic staff or by the subject for at least 60 minutes after drug administration.
	

Abbreviations: eCRF, electronic case report form; NaCl, sodium chloride; SC, subcutaneous.

The contents of the label will be in accordance with all applicable regulatory requirements.

Efficacy and Safety of Imsidolimab in Subjects with Acne Vulgaris
Protocol ANB019-209

Version 1.0
11 February 2021

Table 3: Treatment Administration Schedule

Arm	Day 1 2 x 2 mL ^a	Weeks 4 and 8 1 x 2 mL ^a
1 (400mg/200mg)	2 x 2 mL imsidolimab	1 x 2 mL imsidolimab
2 (200mg/100mg)	1 x 2 mL imsidolimab 1 x 2 mL placebo	1 x 2 mL [imsidolimab (1 mL): placebo (1 mL)]
3 (Placebo)	2 x 2 mL placebo	1 x 2 mL placebo

^a Study treatment will be provided as 1 mL vials of imsidolimab 100 mg/mL or placebo, and 2 mL will be prepared from two individual vials in a covered syringe by an unblinded pharmacist according to the schedule above. The contents of the syringe and the injection procedure will not be visible to subjects.

6.2 PREPARATION/HANDLING/STORAGE/ACCOUNTABILITY

The Investigator or designee must confirm appropriate temperature conditions have been maintained during transit for all study treatments received, and any discrepancies are to be reported and resolved before use of the study treatment.

Only subjects randomized in the study may receive study treatment and only authorized study site staff may supply or administer study treatment. Further guidance and information for the administration of the study treatment are provided in the Pharmacy Manual.

All study treatments must be stored in a secure, environmentally controlled, and monitored (manual or automated) area in accordance with the labeled storage conditions with access limited to the Investigator and authorized study site staff.

Imsidolimab vials must be refrigerated at 2°C to 8°C (36°F to 46°F) until the day of use. Imsidolimab must not be used beyond the re-test or expiration date provided by the manufacturer. Vial contents should not be frozen or shaken. Imsidolimab vials undiluted may be stored at room temperature (8°C to 25°C [46°F to 77°F]) for up to 8 hr. Vials are intended for single use only; therefore, any remaining solution should not be used and should be discarded after study treatment accountability and reconciliation.

The Investigator is responsible for study treatment accountability, reconciliation, and record maintenance (ie, receipt, reconciliation, and final disposition records).

The Investigator, a member of the study site staff, or a hospital Pharmacist must maintain an adequate record of the receipt and distribution of all study medication using the Drug Accountability Form. These forms must be available for inspection at any time.

Further guidance and information for the final disposition of unused study treatment are provided in the Pharmacy Manual.

6.3 MEASURES TO MINIMIZE BIAS: RANDOMIZATION AND BLINDING

This study includes a randomized, double-blind treatment period and safety follow-up period. The blind will be maintained throughout the study with limited and controlled access to the randomization code.

All subjects will be assigned a unique ‘subject identification number’ at the time of screening. On Day 1, after verification that all inclusion and no exclusion criteria have been met, the subjects will be stratified by facial IGA score at baseline (3 [moderate] versus 4 [severe]) and randomized in a 1:1:1 ratio to receive imsidolimab at one of two doses or placebo. As subjects become eligible, they will be assigned unique randomization numbers, which will be used to assign the allocated treatment based on a randomization schedule.

The 400 mg loading dose of imsidolimab will be delivered to subjects in Arm 1 as two 2-mL injections. To maintain the blind, subjects in Arm 2 receiving the 200 mg loading dose will receive one 2-mL injection of imsidolimab and one 2-mL injection of placebo, and subjects assigned to placebo will receive two 2-mL injections of placebo (see [Table 3](#)). At Weeks 4 and 8, subjects will receive 1 x 2 mL injection of either imsidolimab, 1:1 imsidolimab:placebo, or placebo. AnaptysBio, Investigator, and subjects will be blinded to treatment assignment of imsidolimab or placebo. An unblinded Pharmacist will be responsible for study treatment dispensing. Because active study treatment is slightly different in appearance from placebo, syringes will be covered in tape.

Once the subject has provided informed consent/assent and meets all inclusion and no exclusion criteria, the study site will request the treatment assignment using a central Interactive Web Response System (IWRS).

The process for breaking the blind will be handled through the IWRS. Unblinding is undertaken by a predetermined process to ensure that participating subject and study team are not unblinded unnecessarily and the study results are not compromised. Unblinding of treatment assignment during the study should occur only if it is necessary to know what treatment the subject received during the placebo-controlled period. Unblinding should occur if the Investigator deems identification of the study treatment is necessary for the purpose of providing urgent subject care, and knowledge of the subject’s treatment assignment (imsidolimab or placebo) will alter subsequent care (emergency unblinding).

In the event that emergency unblinding is necessary, the Investigator must ensure that the unblinding of the treatment code is performed in a discrete manner and the treatment is disclosed only to those persons involved with the direct medical care of the subject. The Investigator must provide the reason for unblinding to the AnaptysBio Medical Monitor according to AnaptysBio instructions following emergency unblinding.

Efficacy and Safety of Imsidolimab in Subjects with Acne Vulgaris
Protocol ANB019-209

Version 1.0
11 February 2021

AnaptysBio and the contract research organization (CRO) must be notified when a subject and/or Investigator is unblinded during the study. The IWRS will create the blinded and/or unblinded notification when the blind is broken, which can be sent via email as per the user role of IWRS. The unblinding will be captured in the IWRS audit trail. Pertinent information regarding the circumstances of unblinding of a subject's treatment code must be documented in the subject's source documents.

6.4 STUDY TREATMENT COMPLIANCE

Study treatment compliance in this study will be under the direct control of the Investigator; the study treatments will be administered on site.

The prescribed dosage, timing, and mode of administration may not be changed. Any departures from the intended regimen must be recorded in the eCRFs.

For the study treatment administrations, date/time of administration, site of administration, and dose administered (entire dose/incomplete dose) will be documented in the eCRF.

6.5 CONCOMITANT THERAPY

Any medication or vaccine (including over the counter or prescription medicines, vitamins, and/or herbal supplements) that the subject is receiving at the time of enrollment and receives during the study must be recorded on the eCRF along with:

- Reason for use
- Dates of administration including start and end dates
- Dosage information including dose, route, and frequency

In addition, all prior medications used to treat AV disease conditions taken within 6 months prior to enrollment and any other medications taken within 4 weeks prior to enrollment must be recorded in the eCRF. The concomitant treatments for other indications that are not listed in the prohibited therapies or procedures ([Section 6.5.2](#)) must be on a stable dose for at least 4 weeks before study treatment administration (Day 1). Dose adjustments of these treatments should be avoided during the study. Live attenuated vaccines may be utilized after the subjects complete the safety follow-up period of the study. During the follow-up period, no study drug will be administered and 12 weeks (at least three half-lives of study drug) is estimated to be a sufficient period after the last dose administration when a live attenuated vaccine can be safely administered.

The Medical Monitor should be contacted if there are any questions regarding concomitant or prior therapy.

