1.3 SCHEDULE OF ACTIVITIES

The screening evaluation will only be performed after the subject has agreed to participate and has signed and dated the ICF or assent. No treatment or study-related procedures will be initiated before informed consent/assent (when applicable) is signed. The Day 1 visit must be performed, at the latest, 30 days after the screening visit.

The screening evaluation will be performed according to the inclusion and exclusion criteria. If the subject fulfills all inclusion criteria and no exclusion criteria, he or she may be included in the study.

Table 1 provides a description of the procedures to be performed at each visit during the study. Of note, the primary endpoint will be evaluated on Day 85 (Week 12).

Unless specified otherwise, the study assessments scheduled on Day 1 must be performed before study treatment administration. The specific order for performing the study assessments is as follows (applicable to all visits):

- Subject-reported questionnaires
- Efficacy assessments (global assessments [Facial IGA] **must** be performed before more quantitative assessments [lesion count])
- Physical examination
- ECG
- Vital signs
- Blood samples collection (for safety, PK, ADA)
- Photography (may be performed anytime predose provided it is before skin sample collection)
- Tape stripping

The Coronavirus Disease 2019 (COVID-19) pandemic may impact the ability to adhere to the study procedures described in **Table 1** due to challenges that include, but are not limited to, subject preferences, site closures, travel restrictions, and quarantines. Please refer to **Section 4.5** for more details on allowable, as necessary, modifications to the protocol due to COVID-19 restrictions, including conducting optional home visits when on-site study visits are considered not feasible. Such modifications in study conduct always must be in accordance with local regulations/mandates.

Efficacy and Safety of Imsidolimab in Subjects with Acne Vulgaris
Protocol ANB019-209

Version 1.0
11 February 2021

Table 1: Schedule of Activities

Study visit Window (days)	Screening Period (-30 to -1)	Treatment Period					Follow-Up Period D141 (W20) (EOS/ET) ^a (±5)
		D1	D15 (W2) (±2)	D29 (W4) (±4)	D57 (W8) (±4)	D85 (W12) (±4)	
Informed consent/assent ^b	X						
Demographics	X						
Inclusion and exclusion criteria	X	X					
Medical and surgical history	X	X					
Height and weight ^c	X	X					X X
Complete physical examination ^d	X	X		X X			X X

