4 STUDY DESIGN

4.1 OVERALL DESIGN

This is a Phase 2, multicenter, randomized, double-blind, placebo-controlled study to evaluate the efficacy and safety of imsidolimab in adolescent and adult subjects with AV. This study will also characterize the PK profile of imsidolimab and explore the immune response to imsidolimab in subjects with AV.

To be eligible for this study, subjects must be aged 12 to 45 and have moderate to severe facial acne vulgaris at Screening and Day 1, defined as follows:

1. Facial IGA score of 3 (moderate) or 4 (severe).
2. At least 20 and no more than 100 inflammatory lesions on the face.
3. No more than 100 noninflammatory lesions on the face.
4. No more than 5 nodules (≥ 5 mm) on the face.

The maximum study duration per subject is approximately 24 weeks, which includes a screening period of up to 30 days followed by a 12-week treatment period and an 8-week safety follow-up period.

Eligible subjects will be randomized (1:1:1) to receive either imsidolimab (at 1 of 2 different regimens) or placebo, SC administered on 3 occasions: Day 1, Day 29 (Week 4), and Day 57 (Week 8). The randomization will be stratified based on facial IGA score at baseline (3 [moderate] versus 4 [severe]).

The treatment arms will be as follows:

1. Imsidolimab 400 mg on Day 1, followed by 200 mg on Days 29 and 57
2. Imsidolimab 200 mg on Day 1, followed by 100 mg on Days 29 and 57
3. Placebo on Days 1, 29, and 57

For scheduled on-site study visits, subjects will come to the study site on 7 occasions: Screening and Days 1, 15, 29, 57, 85, and 141 (EOS)/ET. All procedures will be conducted in accordance with the SoA in [Section 1.3](#).

Disease activity will be evaluated for all subjects using facial inflammatory and noninflammatory lesion count, Facial IGA, Truncal (chest, neck, and back) PGA, DLQI for subjects ≥ 16 years of age and CDLQI for subjects < 16 years of age, PGIS, PGIC, SSQ, and SSRS.

Safety assessments will include AE/ SAE monitoring, vital signs, physical examination, ECGs, and clinical laboratory tests (hematology, biochemistry, and urinalysis).

Facial photography will be conducted at each study visit. Optional truncal photography will be performed at selected sites.

Blood samples will be collected during the study to determine PK and immunogenicity (presence of ADA to imsidolimab) on Day 1 before the administration of the study treatment and at the

Efficacy and Safety of Imsidolimab in Subjects with Acne Vulgaris

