4.3 JUSTIFICATION FOR DOSE

During the treatment period, imsidolimab will be SC administered as a 400-mg dose on Day 1, followed by 200-mg doses on Days 29 and 57; or as a 200 mg dose on Day 1, followed by 100-mg doses on Days 29 and 57.

The doses selected for the study demonstrated a favorable safety and tolerability profile in a Phase 1 study conducted in healthy volunteers. In addition, imsidolimab demonstrated linear PK with an estimated $t_{1/2}$ of approximately 28 days at all doses tested with persistent pharmacodynamic activity. The loading dose of 400 mg SC administered on Day 1 was chosen to quickly achieve the initial PK exposure needed for response soon after dosing in order to

Efficacy and Safety of Imsidolimab in Subjects with Acne Vulgaris
Protocol ANB019-209

Version 1.0
11 February 2021

provide optimal potential benefit to AV subjects and to reach steady state concentrations rapidly following 200 mg SC dosing. The loading dose of 200 mg SC administered on Day 1 followed by 100 mg doses every four weeks is expected to be lower than the exposure-response curve, allowing for the assessment of dose-dependent effects and to inform dosing in future studies.

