4.4 END OF STUDY DEFINITION

A subject is considered to have completed the study if he or she has completed all periods of the study including the last specified visit (Day 141 [Week 20]/) shown in the SoA ([Section 1.3](#)).

The end of the study is defined as completion of the last visit or procedure shown in the SoA by the last subject included the study.

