 - g. Previous surgical, physical (such as ThermaClear™), light (including blue or UV light, photodynamic therapy [PDT]) or laser therapy within 12 weeks prior to Day 1.
 - h. Cryodestruction, chemodestruction, dermabrasion, acne surgery, intralesional steroids, X-ray therapy procedures performed on the face within 12 weeks prior to Day 1.
 - i. Systemic antibiotics (including tetracyclines) within 4 weeks prior to Day 1.
 - j. Systemic antiviral medication (except for prevention of localized oral or genital herpes simplex) within 4 weeks prior to Day 1.
 - k. Any nonbiologic investigational drug within 4 weeks or 5 half-lives, whichever is longer prior to Day 1.
 - l. Marketed or investigational biological agent within 12 weeks or 5 half-lives (whichever is longer) prior to Day 1.
 - m. Live attenuated vaccine within 12 weeks prior to Day 1, including any approved for COVID-19. Live attenuated vaccines may be utilized after the subjects complete the 8-week standard safety follow-up period of the study. Note: Non-live-attenuated vaccines for COVID-19 (eg, RNA-based vaccines, protein-based vaccines) are allowed during the study.
 - n. Previous treatment with anti-IL-36R, anti-IL-36, anti-tumor necrosis factor (TNF)/IL-12/IL-23/ IL-17, or any other mAbs within 12 weeks or 5 half-lives (whichever is longer) prior to Day 1.
 - o. Oral retinoid (eg, isotretinoin) or vitamin A supplements > 10,000 U/d within 26 weeks prior to Day 1.
 - p. Previous treatment with imidolimab.
17. Has had excessive sun exposure, is planning a trip to a sunny climate, or has used tanning booths within 4 weeks prior to Day 1 or is not willing to minimize natural and artificial

- sunlight exposure during the study. Use of sunscreen products and protective apparel are recommended when sun exposure cannot be avoided.
18. Active TB or latent TB infection as indicated by a positive QuantiFERON®-TB Gold test at screening or within 6 months prior to screening (if the test is indeterminate, it can be repeated only once; chest X-ray will be administered per local standards, as required), and/or clinical examination, or has had active TB disease at any time in the past.
 19. Clinically significant drug or alcohol abuse in the last year prior to Day 1, or other factors limiting the ability to cooperate and to comply with the study protocol, as determined by the Investigator.
 20. Subject is a pregnant or lactating woman, or a woman who intends to become pregnant during the study period.

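### The live-vaccine release rule can clear a fully compliant subject up to 9 days before the 12 weeks since last dose that the protocol gives as its safety basis

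*Protocol*

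**What the plan says.** Protocol Section 6.5 sets the trigger: "Live attenuated vaccines may be utilized after the subjects complete the safety follow-up period of the study". It then gives the reason, that "12 weeks (at least three half-lives of study drug) is estimated to be a sufficient period after the last dose administration" for a live vaccine to be given safely.

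Exclusion criterion 16.m, in the Synopsis and again in Section 5.2, uses the same trigger: "Live attenuated vaccines may be utilized after the subjects complete the 8-week standard safety follow-up period of the study". It does not mention 12 weeks or the date of the last dose.

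Section 4.4 counts a subject as having completed the study when he or she has "completed all periods of the study including the last specified visit (Day 141 [Week 20]/) shown in the SoA". Section 4.3 puts the half-life at "approximately 28 days at all doses tested". Dosing is on Days 1, 29 and 57 (Section 4.1). Table 1 in Section 1.3 gives the Day 57 visit a window of ±4 days and the Day 141 visit a window of ±5 days.

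**The concern.** The rule and its justification are measured from different points. The rule runs to a scheduled visit. The justification runs from the last dose and is stated as a minimum of three half-lives. The two agree only if the time between the last dose and the final visit never falls below 84 days. The nominal schedule gives exactly 84 days, so any net use of the visit windows in the wrong direction breaks the agreement.

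At stake is a subject on an immune-modulating antibody being told that live vaccines are allowed before the interval the protocol itself calls sufficient has passed. This would happen without any protocol deviation to alert anyone. It would also happen as participation ends: Section 6.8 hands care to the subject's own physician, and Section 8.2.1.4 does not oblige investigators to look actively for adverse events afterwards.

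**Working it through.** **Inputs**

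- Last dose: Day 57 ±4, so Day 53 to Day 61 (Protocol Table 1).
- End-of-study visit: Day 141 ±5, so Day 136 to Day 146 (Protocol Table 1).
- Half-life: about 28 days (Protocol Section 4.3).
- Stated basis: 12 weeks = 84 days, at least three half-lives (Protocol Section 6.5).

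**The plan's own figure**

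Nominal interval = 141 − 57 = 84 days = 84/7 = 12.0 weeks = 84/28 = 3.00 half-lives. The stated basis is reproduced, with nothing to spare.

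**Effect of the windows**

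Interval = end-of-study day − last-dose day.

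| Last dose | End of study | Interval (days) | Weeks | Half-lives at 28 days | Against 84 days |
|---|---|---|---|---|---|
| 57 | 141 | 84 | 12.0 | 3.00 | 0 |
| 61 | 136 | 75 | 10.7 | 2.68 | −9 |
| 57 | 136 | 79 | 11.3 | 2.82 | −5 |
| 61 | 141 | 80 | 11.4 | 2.86 | −4 |
| 53 | 146 | 93 | 13.3 | 3.32 | +9 |

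The largest shortfall is 4 days (dose late) + 5 days (visit early) = 9 days. Either window alone is enough to fall short.

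**All in-window schedules**

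There are 9 possible dose days × 11 possible final-visit days = 99 pairs. Of these, 45 give fewer than 84 days (short by 1 to 9), 9 give exactly 84, and 45 give more. The split is symmetric because the nominal interval has no slack. It counts schedules and does not estimate a share of subjects.

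**Other readings of completing follow-up**

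- Eight weeks counted from the earliest Week 12 visit: 81 + 56 = Day 137. After a Day 61 dose this is 137 − 61 = 76 days, 8 short.
- Eight weeks that must elapse from nominal Day 85: 85 + 56 = Day 141. After a Day 61 dose this is 80 days, 4 short.

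**Sensitivity to the half-life**

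Seventy-five days equals three half-lives only if the half-life is 75/3 = 25 days or less. The 12-week figure is missed whatever the half-life.

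**Residual drug**

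Under simple first-order decay with a 28-day half-life, the fraction of the last dose remaining is 2^(−75/28) = 15.6% at 75 days, against 2^(−3) = 12.5% at 84 days.

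**The case against.** The strongest reply is that the 12-week interval already stands in Section 6.5, measured from the last dose and directly after the trigger. An investigator who reads both sentences can apply both, and the section says to ask the Medical Monitor when in doubt. This has some force for Section 6.5 read alone. But the sentence explains why the trigger is acceptable and does not impose a separate wait. Criterion 16.m omits it in both places and speaks only of an 8-week follow-up, so a site working from the eligibility criteria sees no 12-week requirement.

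A second reply is that completion of an 8-week period may mean that all eight weeks have elapsed. On that reading the worst case is 4 or 8 days instead of 9. This is fair, and it narrows the gap, but no reading removes it.

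A third reply is that the benchmark is soft. The sufficiency of 12 weeks is an estimate, the half-life is approximate, and nine days is about a third of a half-life (9/28 = 0.32). Nothing in the documents says the difference in residual drug matters. Section 2.3.1 also states that blocking the receptor does not generally weaken host defences, although the same section advises monitoring for infection and reports a possibly related serious event of sepsis. Harm would need a late dose, an early final visit and a live vaccine within days of it. All of this stands, and it is why the point is a small one.

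Finally, visit windows always make intervals flex. That is true, but a safety interval stated as a minimum should hold throughout the windows the protocol itself allows.

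**Conclusion.** The concern holds. As written, the trigger does not guarantee the interval that Section 6.5 offers as its justification. A compliant subject can be released 75 to 93 days after the last dose, so up to 9 days before 12 weeks and at as little as 2.68 half-lives.

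This rests on three assumptions: the windows are anchored to Day 1, as the day numbers in Table 1 read; completion means attending the final visit, as in Section 4.4; and the half-life is 28 days for the half-life figures. No text was found that ties the final visit, or the release of vaccines, to the actual last-dose date.

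The consequence is modest. The protocol does not say that a shorter interval is unsafe, and efficacy analysis, power and type I error are unaffected. It is worth correcting because a stated safety basis should be true for every subject who completes follow-up, and making it so costs almost nothing.

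**What to change.** Replace the trigger in Section 6.5 and in criterion 16.m (Synopsis and Section 5.2) with wording such as:

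> *Live attenuated vaccines are permitted after safety follow-up has ended and at least 12 weeks after the last dose the subject actually received, whichever is later.*

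Add one line to the end-of-study instructions: tell the subject the earliest permitted date, because any remaining wait falls after the last visit. Dose dates are already recorded in the eCRF (Section 6.4). Counting from the dose actually given also has a precedent here, since male contraception runs 200 days from the last administration (Section 5.1).

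The cost is one sentence in three places and one line of instruction. A subject dosed on Day 61 would be cleared on Day 61 + 84 = Day 145, still inside the existing final-visit window. The longest extra wait for an in-window subject is 145 − 136 = 9 days, with no added visit or procedure.
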